10. SAFETY ANALYSES

10.1 Maternal Adverse Events

In addition to the summaries of the primary maternal safety endpoint detailed in Section 8.1, maternal adverse event summaries will include:

- the total number and percentage of participants with an SAE
- the total number of SAEs by severity grade and relationship to study product
- the total number of composite AEs by severity grade and relationship to study product
- the number and percentages of composite AEs for each level of relationship to study product (not related, related) for the most causal relationship per participant overall and by system organ class and preferred term.
- the number and percentage of participants with any AE, and number and percentage of AEs by body system, preferred term, and severity
- the number and percentage of participants with any AE, and number and percentage of AEs by body system, preferred term, and relationship to study product
- listing of all AEs, including participant ID, cohort, randomization arm, site, whether or not the AE was an SAE, whether or not the AE was a composite AE, preferred term, severity, relationship to study product, visit of AE report, AE onset date, AE outcome date, AE duration, AE outcome, and associated comments.
- the above summaries will be repeated using the Product Exposure Set

The denominator for all percentages described above is the number of participants in the analysis set. All summaries will be presented by arm across all cohorts, and by arm within each cohort. No statistical comparisons are planned.

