8. PRIMARY ENDPOINTS

An intent to treat analysis will be performed to summarize the frequency of primary endpoints (maternal safety, infant safety and pregnancy outcome) by study arm (ITT Analysis Set). An additional analysis will be conducted including only visits in which a participant has been exposed to the study product (Product Exposure Set). Analyses will be conducted separately for each of the three cohorts (including an exploratory analysis that splits Cohort 3 based on gestational age as described in Section 5), with a final aggregate analysis that will include all enrolled participants from each of the three cohorts. The number and the percentages of participants experiencing each primary endpoint will be tabulated by study arm. Each participant will contribute once in each category (i.e., only for highest severity AE for each

participant) for the calculation of event rates. Exact binomial confidence intervals will be calculated for each primary endpoint. Primary endpoint event rates will be compared to baseline estimates from MTN-042B by checking whether the baseline estimates are included in the exact binomial confidence intervals (this will not be included as part of the CSR). A secondary analysis will be performed to summarize the total number of primary and secondary safety endpoints reported per participant by study arm.

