10.2 Infant Adverse Events

In addition to the summaries of the primary infant safety endpoint detailed in Section 8.2, infant adverse event summaries will include:

- the total number and percentage of infants with an SAE
- the total number of infant SAEs by severity grade and relationship to study product
- the total number of infant composite AEs by severity grade and relationship to study product
- the number and percentages of infant composite AEs for each level of relationship to study product (not related, related) for the most causal relationship per participant overall and by system organ class and preferred term.
- the number and percentage of participants with any AE, and number and percentage of AEs by body system, preferred term, and severity
- the number and percentage of participants with any AE, and number and percentage of AEs by body system, preferred term, and relationship to study product
- listing of all infant composite AEs, including participant ID, cohort, mother's randomization arm, site, whether or not the AE was an SAE, preferred term, severity, relationship to study product, visit of AE report, AE onset date, AE outcome date, AE duration, AE outcome, and associated comments.
- the above summaries will be repeated using the Infant Exposure Analysis Set

The denominator for all percentages described above is the number of infants in the analysis set. All summaries will be presented by arm across all cohorts, and by arm within each cohort. No statistical comparisons are planned.

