10.3 Product Holds

The number and percentage of participants who had at least one product hold, the total number of product holds, the number and percentage of reasons for product hold, the number and percentage of the instructions whether to resume study product use, and the duration of product hold (for those holds where the participant was instructed to resume use) will be summarized in tables. These tables will be presented by arm and overall for each of the three cohorts, and by arm and overall for the three cohorts combined. Product holds are collected on the Product Hold CRF.

The denominator for the percentage of participants with at least one product hold will be the number of mothers in the analysis set. The denominator for the other percentages will be the total number of product holds. The duration of product hold will be summarized as a continuous variable (see Section 5 General Analysis Methods).

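### Two bullets in each of SAP 10.1 and 10.2 divide counts of AEs by counts of people, so the printed percentage is AEs per person and can pass 100%

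*SAP*

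**What the plan says.** SAP 10.1 lists the maternal AE summaries. The fifth bullet asks for "the number and percentage of participants with any AE, and number and percentage of AEs by body system, preferred term, and severity". The sixth repeats the pattern and ends with "number and percentage of AEs by body system, preferred term, and relationship to study product". In both, participants with any AE are named first and AEs are named as a second, separate quantity.

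Below the list, one rule covers every percentage: "The denominator for all percentages described above is the number of participants in the analysis set". SAP 10.2 has the same two bullets for infants and the parallel rule: "The denominator for all percentages described above is the number of infants in the analysis set". Both sections repeat the tables in the matching exposure set.

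Two other passages bear on the unit of counting:
- The fourth bullet in each section, on composite AEs by relationship, limits itself to one entry per person: "for the most causal relationship per participant overall and by system organ class and preferred term".
- SAP section 8, on the primary endpoints, says "Each participant will contribute once in each category" when event rates are calculated. Sections 10.1 and 10.2 do not refer to it.

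Elsewhere the SAP keeps the two units apart. In 10.3, the percentage of women with a hold is taken over mothers, and then "The denominator for the other percentages will be the total number of product holds". Section 6.3 puts types of deviation over the number of deviations. Sections 7.4, 10.9 and 10.17 attach percentages to people and give event totals as plain counts for the corresponding items.

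**The concern.** An event count over a person count is neither a share of events nor a proportion of people. A woman with three AEs in one body system adds three to the numerator and one to the denominator. A reader of a safety table will normally take a percentage beside a preferred term as the share of women or infants affected. That reading would be too high in every category where AEs recur.

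The stated primary objective is to describe maternal and infant safety, and these are the tables that break AEs down by body system and preferred term. The maternal listing covers all AEs with participant ID, so a reader with access to it could rebuild person-level figures. The infant listing covers composite AEs only. For non-serious infant AEs below Grade 3, the affected tables are therefore the only planned breakdown by category.

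**Working it through.** The SAP states no figure on this point, so there is nothing to reproduce. The check is one of definitions, followed by arithmetic on assumed counts.

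**1. What the cell contains.** With N people in the analysis set and E AEs in a category, the literal cell is 100 × E / N, which is 100 times the mean number of AEs per person. Two coherent alternatives are 100 × (people with at least one AE) / N and 100 × E / (all AEs).

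**2. When it passes 100%.** This happens as soon as E exceeds N. With planned sizes from SAP 2.6:
- n=50: 51/50 = 102.0%
- n=150: 151/150 = 100.7%
- n=400: 401/400 = 100.25%

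**3. One worked cell (assumed counts).** Take one preferred term with 60 AEs in 40 of 400 women, and 1,000 AEs in all.
- Literal rule: 60/400 = 15.0%
- Women affected: 40/400 = 10.0%
- Share of AEs: 60/1,000 = 6.0%
- All-AE row under the literal rule: 1,000/400 = 250%

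**4. Size over a range.** Let m be the assumed mean number of AEs per person in a category. The share of people with at least one AE is 1 − exp(−m) if counts are Poisson, and m/(1 + m) if they are overdispersed (gamma-Poisson, shape 1).

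| m | Printed | Affected, Poisson | Affected, overdispersed | Printed ÷ affected |
|---|---|---|---|---|
| 0.05 | 5% | 4.9% | 4.8% | 1.03 to 1.05 |
| 0.3 | 30% | 26% | 23% | 1.16 to 1.30 |
| 0.5 | 50% | 39% | 33% | 1.27 to 1.50 |
| 1 | 100% | 63% | 50% | 1.58 to 2.00 |
| 2 | 200% | 86% | 67% | 2.31 to 3.00 |

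The distortion is negligible for rare terms and large for all-AE totals or broad body systems.

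**5. Pooled maternal columns.** SAP 2.1 gives maternal participation of up to about 12 weeks in Cohort 1 and up to about 36 weeks in Cohort 3. It gives no figure for Cohort 2, so let it be x, assumed between 12 and 36. The planned ring arm is 100, 100 and 200 women across the cohorts; the tablet arm is 50, 50 and 50.
- Ring mean: 0.25 × 12 + 0.25x + 0.5 × 36 = 21 + 0.25x
- Tablet mean: (12 + x + 36)/3 = 16 + x/3
- x = 12: 24 against 20 weeks, ratio 1.20
- x = 36: 30 against 28 weeks, ratio 1.07

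At equal AE rates per week, the literal percentage in the pooled ring column would be 7% to 20% higher, in relative terms, through follow-up alone. A person-level percentage would differ too, but by less, because each person counts at most once.

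**The case against.** The strongest reply is that the authors meant a person-level table. There is some support for this. The fourth bullet also speaks of percentages of composite AEs yet plainly takes one entry per person, so naming AEs does not by itself settle the unit. The second and third bullets, which clearly want event totals, ask for no percentage. The section 8 rule speaks of the highest-severity AE per participant, although 8.1 and 8.2 tabulate no severity categories. A programmer could reasonably carry that rule forward.

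This shows what may have been intended, but it does not repair the text. The rule is stated for primary endpoint rates, and 10.1 and 10.2 do not invoke it. Where those sections want one entry per person they say so, and the two bullets at issue do not. They also set the AE count beside a separate participant count. Two programmers could produce different tables from the same words.

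Other limits stand in full:
- The magnitudes rest on assumed AE rates. A mean of 1 or 2 per person is conceivable for an all-AE total, and much less so for a preferred term within one severity grade.
- The tables supplement 8.1 and 8.2, and no statistical comparisons are planned for them.

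A reader might infer that the primary safety results are distorted. They are not: 8.1 and 8.2 count people with at least one composite AE. A reader might also infer that unequal follow-up distorts every arm and cohort column. The SAP does not support that. Infants are followed for about 52 weeks in every cohort, and arms randomised within a cohort have the same planned follow-up. The issue is confined to cross-cohort and pooled maternal columns.

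**Conclusion.** The point holds for the two bullets on the number and percentage of AEs in each of 10.1 and 10.2. Followed as written, they print AEs per person as a percentage. That overstates the share affected wherever AEs recur: by about 3% to 5% in relative terms at an assumed mean of 0.05, by 27% to 50% at 0.5, and with values above 100% once AEs outnumber people. These sizes assume Poisson or gamma-Poisson counts; the unit mismatch itself needs no assumption.

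The percentages of participants with any AE or with an SAE are correct with this denominator, and the composite-AE-by-relationship bullet already reduces to one entry per person. This is a reporting defect in descriptive safety tables. It should be corrected, but it does not threaten the primary analysis.

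**What to change.** In the fifth and sixth bullets of 10.1 and 10.2, ask for the number and percentage of participants (infants) with at least one AE in each body system and preferred term. Count each person once per category, at highest severity in the severity table and at most causal relationship in the relationship table, and keep the analysis set as the denominator. Report the number of AEs beside it as a count only, or as a percentage of all AEs with that denominator named.

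This does not remove the dependence on follow-up length in cross-cohort and pooled maternal columns, because the chance of at least one AE also rises with time on study.

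The cost is SAP wording and table shells. No new data are needed.

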10.2 Infant Adverse Events

In addition to the summaries of the primary infant safety endpoint detailed in Section 8.2, infant adverse event summaries will include:

- the total number and percentage of infants with an SAE
- the total number of infant SAEs by severity grade and relationship to study product
- the total number of infant composite AEs by severity grade and relationship to study product
- the number and percentages of infant composite AEs for each level of relationship to study product (not related, related) for the most causal relationship per participant overall and by system organ class and preferred term.
- the number and percentage of participants with any AE, and number and percentage of AEs by body system, preferred term, and severity
- the number and percentage of participants with any AE, and number and percentage of AEs by body system, preferred term, and relationship to study product
- listing of all infant composite AEs, including participant ID, cohort, mother's randomization arm, site, whether or not the AE was an SAE, preferred term, severity, relationship to study product, visit of AE report, AE onset date, AE outcome date, AE duration, AE outcome, and associated comments.
- the above summaries will be repeated using the Infant Exposure Analysis Set

The denominator for all percentages described above is the number of infants in the analysis set. All summaries will be presented by arm across all cohorts, and by arm within each cohort. No statistical comparisons are planned.

10.3 Product Holds

The number and percentage of participants who had at least one product hold, the total number of product holds, the number and percentage of reasons for product hold, the number and percentage of the instructions whether to resume study product use, and the duration of product hold (for those holds where the participant was instructed to resume use) will be summarized in tables. These tables will be presented by arm and overall for each of the three cohorts, and by arm and overall for the three cohorts combined. Product holds are collected on the Product Hold CRF.

The denominator for the percentage of participants with at least one product hold will be the number of mothers in the analysis set. The denominator for the other percentages will be the total number of product holds. The duration of product hold will be summarized as a continuous variable (see Section 5 General Analysis Methods).

10.4 Mother Laboratory Evaluations

Results of mother laboratory evaluations will be summarized for the following tests: hemogram (hemoglobin, hematocrit, MCV, platelets, WBC, neutrophils, lymphocytes, monocytes, eosinophils, and basophils) test results as collected on the Hematology CRF, chemistries (AST, ALT, creatinine, and creatinine clearance) test results as collected on the Chemistry Panel CRF, and dipstick urinalysis (leukocyte esterase, nitrites, protein, and glucose) test results as collected on the Urine Test Results CRF. Boxplots (for continuous variables, i.e., hemogram and chemistries) and tables with summary statistics (for all) will be reported for laboratory evaluations performed at expected visits. These summaries will be by visit, by arm and overall for each of the three cohorts, and by visit, by arm and overall for the three cohorts combined. Results from non-expected visits, including interim visits, will not be summarized in the boxplots or summary tables.

Expected visits for hemogram, chemistries (AST and ALT), and dipstick urinalysis are the following:

- Screening (visit 1)
- Enrollment (visit 2)
- first 4-week visit (visit 6; this visit only for Cohorts 2 and 3)

- the visit corresponding to, or immediately following, the 28th week of gestation (only for Cohort 3; this is visit 10 if the participant had a gestational age of 20-23 weeks at enrollment, visit 14 if the gestational age was 16-19 weeks, or visit 18 if the gestational age was 12-15 weeks, all according to the Pregnancy Assessment CRF, see Section 3.2 Statistical Analysis Issues)
- 6-week PPO visit/SEV/early SEV (visit 103)

The results for the 28th week of gestation visit will be reported as one visit (i.e., not reported separately for visit 10, visit 14, and visit 18).

Expected visits for creatinine and creatinine clearance are the following:

- Screening (visit 1)
- Enrollment (visit 2)
- second bi-weekly visit/first 4-week visit (visit 6)
- 4-week visit 12 weeks after first 4-week visit (Cohorts 2 and 3 only; visit 18)
- 6-week PPO visit/SEV/early SEV (visit 103)

10.5 Infant Laboratory Evaluations

Boxplots and tables with summary statistics will be reported for infant creatinine results at expected visits. These summaries will be by visit, by mother randomization arm and overall for each of the three cohorts, and by visit, by arm and overall for the three cohorts combined. Results from non-expected visits, including interim visits, will not be summarized in the boxplots or summary tables. Creatine test results were expected at the PPO visit (visit 201) and at the 6-week PPO visit (visit 203).

10.6 Mother HIV-1

Tables summarizing the number and percentage of participants with post-enrollment HIV-1 diagnosis will be prepared. A participant will be considered to have been diagnosed with HIV-1 if they have an HIV Confirmatory Results CRF with a “Final HIV Status” of HIV infected at any visit after Enrollment. The denominator will be the number of participants in the analysis set with at least one post-Enrollment visit HIV Test Results CRF indicating that a rapid HIV test sample collected for testing. These tables will be presented by study arm and overall for each of the three cohorts, and by arm and overall for the three cohorts combined.

10.7 Infant HIV-1

Tables summarizing the number and percentage of infants with an HIV-1 diagnosis will be prepared. An infant will be considered to have been diagnosed with HIV-1 if they have an Infant HIV Confirmatory Results CRF with a “Final HIV Status” of HIV infected. The denominator will be the number of infants in the analysis set. These tables will be presented by study arm and overall for each of the three cohorts, and by study arm and overall for the three cohorts combined.

10.8 Sexually Transmitted Infections

The number and percentage of participants diagnosed with syphilis, trichomonas, gonorrhea, or chlamydia, as well as the number and percentage diagnosed with any of those four STIs during follow-up will be summarized in tables, by arm and overall for each of the three cohorts, and by arm and overall for the three cohorts combined. These will be summarized using the STI Test Results CRF from follow-up visits (e.g., Week 1 Phone Contact/Visit 3 or later).

A positive result for trichomonas, gonorrhea, or chlamydia is defined as having a value of “Positive” for “Trichomonas test”, “N. gonorrhoea”, or “C. trachomatis” respectively, and a negative result as having a value of “Negative”. A positive result for syphilis is defined as having a value of “Reactive” for “Syphilis

screening test" and a value of "Positive" for "Syphilis confirmatory test", and a negative result if the syphilis test was done but did not meet the above definition for positivity. If "Was a vaginal sample collected for NAAT for GC/CT/Trich testing?" is "No" or the response to "Trichomonas test" is "Not done" or missing the participant will not be counted in the denominator for trichomonas. If "Was a vaginal sample collected for NAAT for GC/CT/Trich testing?" is "No" or the response to "N. gonorrhea" is "Not done" or missing the participant will not be counted in the denominator for gonorrhea, and if "Was a vaginal sample collected for NAAT for GC/CT/Trich testing?" is "No" or the response to "C. trachomatis" is "Not done" or missing the participant will not be counted in the denominator for chlamydia.

Participants will be categorized as a positive result if they ever had a positive result during follow-up (e.g., participants will only be counted once per STI). Participants will be categorized as a negative result for each if they had at least one test result during follow-up and no positive results.

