2.1 General Design Considerations

The following is a summary of Protocol Version 2.0

Short Title:	DELIVER: A Phase 3b Safety Study of the Dapivirine Ring and PrEP in Pregnant Women
IND Sponsor:	DAIDS
Funders:	Division of AIDS, NIAID, NIMH, NICHD, US NIH
Protocol Chair:	[name], MPH [name], MMed
Protocol Co-Chair:	[name], FCPaeds
Sample Size:	Approximately 550 women and their infants
Study Population:	Healthy, HIV-uninfected pregnant females, 18-40 (inclusive) years old, with an uncomplicated singleton pregnancy who are willing to be randomized to study product, and their infants
Study Sites:	MTN-042 site(s) selected by the MTN Executive Committee
Study Hypotheses:	
 • Daily use of Truvada oral tablet and dapivirine (DPV) vaginal matrix ring (25 mg) inserted once every 4 weeks will both be generally safe and well-tolerated by the participants and their fetuses/infants. • Participants who use Truvada oral tablet daily and insert the DPV vaginal matrix ring (25 mg) once every 4 weeks will experience similar distributions of pregnancy outcomes to the general population.
Study Design:	Phase 3b, two-arm, open label, multi-site, randomized (2:1) trial (DPV vaginal ring [VR], Truvada oral tablet), with onset of dosing period to occur within the following gestational age (GA) ranges: 
Cohort 1: 36 0/7 weeks – 37 6/7 weeks 150 women Cohort 2: 30 0/7 weeks – 35 6/7 weeks 150 women Cohort 3: 12 0/7 weeks – 29 6/7 weeks 150 women

Study Duration:	The total duration of study participation for each participant will vary depending on gestational age at time of enrollment and length of pregnancy prior to pregnancy outcome, and will range from approximately 12 weeks or less for Cohort 1 to approximately 36 weeks or less for Cohort 3. Participants who

become infected with HIV will continue in study follow-up with a modified study visit/procedure schedule for a minimum of twelve months. Also, infants born to MTN-042 participants will be followed for approximately 52 weeks (i.e., one year)

Study Products:

- Silicone elastomer matrix VR containing 25 mg of DPV
- Oral tablets (Truvada) containing 200 mg emtricitabine/300 mg tenofovir disoproxil fumarate (FTC/TDF)

Study Regimen:

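### Section 10.8 tabulates a woman with a reactive syphilis screen and no confirmatory result as syphilis-negative

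*SAP*

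**What the plan says.** SAP section 10.8 tabulates, by arm and overall, the women diagnosed during follow-up with each of four infections and with any of the four.

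- **Syphilis, positive.** Two fields must agree: a reactive screening test and a positive confirmatory test.
- **Syphilis, negative.** The record is "a negative result if the syphilis test was done but did not meet the above definition for positivity".
- **Trichomonas, gonorrhea, chlamydia.** Positive and negative each require that explicit value on a single field. If no vaginal sample was collected, or the result is not done, "or missing the participant will not be counted in the denominator for trichomonas". Parallel wording covers gonorrhea and chlamydia.
- **Participant level, all four infections.** One positive during follow-up makes the woman positive. Otherwise: "Participants will be categorized as a negative result for each if they had at least one test result during follow-up and no positive results".

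The section has no unconfirmed or indeterminate syphilis category. It gives no rule for a confirmatory test that is missing or not done.

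**The concern.** Requiring confirmation before counting a syphilis diagnosis is reasonable. The difficulty lies on the other side of the definition: negative is not defined by a result but is the remainder once confirmed positives are taken out. A woman whose screen is reactive and whose deciding second test is absent has unknown status, yet the rule gives her the same label as a woman with a non-reactive screen.

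She then stays in the syphilis denominator as uninfected, and syphilis contributes nothing for her to the row for any of the four infections. A reader of the table cannot tell how many of the negatives are of this kind. If any of them were in fact infected, the count of cases is too low; the rule cannot make it too high. The other three infections in the same table do not have this feature, so the word negative carries two meanings within one table.

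**Working it through.** The SAP gives no figure for this rule, so there is nothing to reproduce. The check is to list the possible syphilis records and apply section 10.8 as written.

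| Screening test | Confirmatory test | Class under section 10.8 |
|---|---|---|
| Non-reactive | none needed | negative |
| Reactive | positive | positive |
| Reactive | negative | negative |
| Reactive | missing or not done | a test was done, positivity not met: **negative** |
| Not done | not done | not classified |

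The fourth row is the problem. The participant-level rule carries it forward: the woman has a test result and no positive one, so she is negative overall unless another follow-up visit gives a confirmed positive.

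*Does a stricter reading of the phrase about the test being done remove the problem?* If it meant that both tests were always done, a non-reactive screen with no confirmatory test (first row) could not be negative either. That would leave most tested women unclassified, so the phrase must be satisfiable by the screening test alone. The fourth row then satisfies it too.

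*Possible size, as an illustration only.* Inputs:

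- N = 550 women, from section 2.1 ("Approximately 550 women and their infants"). This is planned enrolment, used here as if all had a follow-up syphilis test.
- c = 10 confirmed positives. Assumed; not in the SAP.
- u = 1, 5 or 10 women reactive without a confirmatory result. Assumed; not in the SAP.

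Formulas: as written, c/N; with unresolved women out of the denominator, c/(N − u); upper limit if every unresolved woman were infected, (c + u)/N.

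| u | As written | Unresolved excluded | Upper limit |
|---|---|---|---|
| 1 | 10/550 = 1.82% | 10/549 = 1.82% | 11/550 = 2.00% |
| 5 | 10/550 = 1.82% | 10/545 = 1.83% | 15/550 = 2.73% |
| 10 | 10/550 = 1.82% | 10/540 = 1.85% | 20/550 = 3.64% |

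Excluding unresolved women changes the percentage by at most 0.03 points here. The distance between the second and last columns shows what the table conceals as written: a reader who is not told u cannot form the upper limit.

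**The case against.** **The phrase could mean a completed test sequence.** On this reading, testing is done when the screen is non-reactive, or when a reactive screen has been followed by a confirmatory result; reactive-unconfirmed women would then be unclassified. It is a sensible intention, but section 10.8 does not say it and nothing elsewhere in the SAP supplies it. A programmer following the text would code negative.

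**The contrast with the other three infections is not exact.** They rest on one field each, so they have no missing second stage, and syphilis also leaves out women with no test at all. Both points are correct. What remains is that the other infections require an explicit Negative value, whereas syphilis accepts the absence of the deciding result.

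**HIV is the closer parallel.** Section 10.6 counts only infections confirmed by a final status and keeps every woman with a rapid test sample collected in the denominator. This supports requiring confirmation for a case. But section 10.6 reports diagnosed women over tested women and does not declare the rest negative; section 10.8 does.

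**The change leaves the numerator as it is.** This stands. A reader might infer that the syphilis frequency is materially understated and that exclusion would correct it. The documents do not support the first part, since they give no number of unresolved women. The illustration contradicts the second, since the estimate barely moves. The footnoted count is what adds information.

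**Nothing important depends on it.** This also stands. STIs are neither a primary nor a secondary endpoint in section 2.2. The Poisson models in sections 8.1 and 8.2 adjust for site only, and the pregnancy outcomes in section 8.3 are plain proportions. A reader might infer that misclassified syphilis distorts the pregnancy or infant results, but no analysis in the SAP uses STI status.

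**Conclusion.** The point holds as a small misclassification written into section 10.8: a reactive syphilis screen with a missing or not-done confirmatory test is tabulated as negative. This follows from the wording and needs no assumption about the data.

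Its size is unknown. The SAP does not report how often confirmatory results are absent, and the number may be zero. A reader could multiply 550 women by an assumed 1–4% reactive and 10–30% of those unconfirmed, giving 550 × 0.01 × 0.10 = 0.6 to 550 × 0.04 × 0.30 = 6.6 women. Neither rate has any basis in the SAP, and 550 is planned enrolment rather than women tested, so that range should not be cited as a finding.

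The consequence is limited to one descriptive safety table. It is worth correcting because the correction is cheap and because unresolved reactive results should not be reported as uninfected.

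**What to change.** In section 10.8, replace the residual definition of syphilis-negative with an explicit one:

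- Negative: a non-reactive screening test, or a reactive screening test with a negative confirmatory test.
- Reactive with the confirmatory test missing or not done: no valid syphilis result at that visit. The woman leaves the syphilis denominator unless another follow-up visit gives a valid result.
- In the participant-level rule, require at least one valid result.
- Footnote the number of reactive-unconfirmed women by arm, on the syphilis row and on the row for any of the four infections, so that the possible range can be seen.

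This uses fields the section already names and needs no new data. It costs a sentence or two in the SAP and a footnote, and the syphilis denominator may fall by a few women. If no such records exist, the tabulated figures do not change.
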